APPENDIX 6. PROMIS INSTRUMENTS

PROMIS Item Bank v1.0 – Dyspnea Severity – Short Form 10a

Dyspnea Severity – Short Form 10a

Please respond to each question or statement by marking one box per row.

Over the past 7 days, how short of breath did you get with each of these activities?...		No shortness of breath	Mildly short of breath	Moderately short of breath	Severely short of breath	I did not do this in the past 7 days
DYSSV001	Dressing yourself without help	 0	 1	 2	 3	 X
DYSSV002	Walking 50 steps/paces on flat ground at a normal speed without stopping.....	 0	 1	 2	 3	 X
DYSSV003	Walking up 20 stairs (2 flights) without stopping.....	 0	 1	 2	 3	 X
DYSSV004	Preparing meals.....	 0	 1	 2	 3	 X
DYSSV005	Washing dishes	 0	 1	 2	 3	 X
DYSSV006	Sweeping or mopping	 0	 1	 2	 3	 X
DYSSV007	Making a bed.....	 0	 1	 2	 3	 X
DYSSV008	Lifting something weighing 10-20 lbs (about 4.5-9kg, like a large bag of groceries).....	 0	 1	 2	 3	 X
DYSSV009	Carrying something weighing 10-20 lbs (about 4.5-9kg, like a large bag of groceries) from one room to another.....	 0	 1	 2	 3	 X
DYSSV010	Walking (faster than your usual speed) for $\frac{1}{2}$ mile (almost 1 km) without stopping.....	 0	 1	 2	 3	 X

PROMIS Item Bank v1.0 – Fatigue – Short Form 8a

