9.5. Patient-reported Outcomes

For each PRO instrument including R-PAct scale, RHS, FSS, and PROMIS scales, the total score is obtained by summing up the individual scores. Summaries will be provided at baseline, Visit 12 and every 3 months in Stage 3, and every 6 months in Stage 4. The actual total score, absolute change, and percent change from baseline in the total score at each visit will be summarized at each visit. The PROMIS scale was introduced in the middle of the study and so baseline scores will not be available. A subject listing of each individual PRO will be provided.

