9.7. Handling of Dropouts or Missing Data

The efficacy and safety analysis will be based on observed values. However, summary at the LAV will be provided for the efficacy analyses (see Section [6.5](#)).

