The total score ranges from 9 to 36, with higher values representing lower level of handicap. The total score is obtained as the sum of the individual scores, and it will be analyzed as a continuous variable. The instrument will be scored using the traditional 50% response rule, described as follows:

If a score of '0 = not applicable' is provided, it is interpreted as a missing response or an unanswered question.

If $\geq 50\%$ of the questions were answered (ie, at least 5 out of 9 responses are available), the total score is obtained as: Total = $([\text{Sum of all available scores}] \times 9) / (9 - [\text{Number of missing items}]) = (\text{Mean of all available scores}) \times 9$ ([Merkies, Schmitz et al. 2002](#)).

Otherwise (ie, if less than or equal to 4 out of 9 questions were answered), the total score will be considered missing ('.').

9. Fatigue Severity Scale (FSS): This consists of 9 questions, each scored on a scale from 1 = ‘completely disagree’ to 7 = ‘completely agree.’

The total score ranges from 9 to 63, with higher values representing higher level of fatigue due to the disease condition. The total score is obtained as the sum of the individual scores, and it will be analyzed as a continuous variable. The 50% response rule will be applied.

If at least 5 out of 9 item responses are available, the total score will be calculated as: $\text{Total} = ([\text{Sum of all available scores}] \times 9) / (9 - [\text{Number of missing items}]) = (\text{Mean of all available scores}) \times 9$. Otherwise, the total is considered missing.

10. PROMIS® Short Forms:

- PROMIS – Physical Function Short Form 20a (v2.0) consists of 20 questions. The first 14 questions are each scored on a scale from 1 to 5 as follows: 1 = unable to do; 2 = with much difficulty; 3 = with some difficulty; 4 = with a little difficulty; 5 = without any difficulty; the next 6 questions are each scored on a scale from 1 to 5 as follows: 1 = cannot do; 2 = quite a lot; 3 = somewhat; 4 = very little; 5 = not at all.

The total score ranges from 20 – 100, with higher scores indicating more mobility.

- PROMIS – Fatigue Short Form 8a consists of 8 questions, each scored on a scale from 1 to 5 as follows: 1 = not at all; 2 = a little bit; 3 = somewhat; 4 = quite a bit; 5 = very much; and 2 questions, each scored on a scale from 1 to 5 as follows: 1 = never; 2 = rarely; 3 = sometimes; 4 = often; 5 = always.

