The total score ranges from 8 – 40, with higher scores indicating more fatigue.

- PROMIS – Upper Extremity Short Form 7a consists of 7 items each scored on a decreasing scale from 1 to 5 as follows: 1 = unable to do; 2 = with much difficulty; 3 = with some difficulty; 4 = with a little difficulty; 5 = without any difficulty.

The total score ranges from 7 – 35, with higher scores indicating less disability in the upper extremity.

- PROMIS – Dyspnea Severity Short Form 10a consists of 10 questions each scored on a scale from 0 to 3 as follows: 0 = no shortness of breath; 1 = mildly short of breath; 2 = moderately short of breath; 3 = severely short of breath.

The total score ranges from 10 – 50, with higher scores indicating greater shortness of breath.

The total score of each PROMIS instrument is obtained by summing up the individual scores, and it will be analyzed as a continuous variable.

11. Global impression of change

- SGIC: The Subject’s Global Impression of Change involves 8 questions assessing each of the following functional areas:
 - overall physical wellbeing
 - effort of breathing

- muscle strength
- muscle function
- ability to move around
- activities of daily living
- energy level
- level of muscular pain

Each of the 8 functional items is scored on a 7-point rating scale as follows: 1 = very much worse; 2 = much worse; 3 = worse; 4 = no change; 5 = improved; 6 = much improved; 7 = very much improved.

For each functional item, a ternary response is defined as: “Improved” = item response of 5 or higher, ‘No change’ = item response of 4, or “Declining” = item response of 3 or lower.

- PGIC: The Physician’s Global Impression of Change (PGIC) is based on a single question that is scored on a 7-point rating scale, similarly to the SGIC.
A ternary response is created from the responses, defined as: “Improved” = response of 5 or higher, “No change” = response of 4, or “Declining” = response of 3 or lower.

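### The PROMIS Dyspnea total has no rule for activities not done, so it mixes activity level with breathlessness, and its stated range is impossible

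*SAP*

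**What the plan says.** **The form.** Protocol Appendix 6 shows Dyspnea Severity Short Form 10a with five responses per item. Four are numbered 0 to 3. The fifth is "I did not do this in the past 7 days", marked X. The items include two flights of stairs, carrying 10 to 20 lb, and a fast half-mile walk.

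**The scoring.** SAP Appendix 1, item 10, says the form "consists of 10 questions each scored on a scale from 0 to 3 as follows: 0 = no shortness of breath", and continues up to 3 for severe. X is not mentioned. The total follows from "The total score of each PROMIS instrument is obtained by summing up the individual scores". SAP Section 9.5 repeats this for every patient-reported instrument: "the total score is obtained by summing up the individual scores". The same bullet gives the range: "The total score ranges from 10 – 50, with higher scores indicating greater shortness of breath".

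**The neighbouring scales.** For the Rotterdam Handicap Scale (RHS, item 8), a not-applicable answer has a stated treatment: "it is interpreted as a missing response or an unanswered question". The total is then prorated if at least 5 of 9 items are answered and set to missing otherwise. For the Fatigue Severity Scale (FSS, item 9): "The 50% response rule will be applied". No such rule is given for any PROMIS form.

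**Missing data in general.** SAP Section 9.7: "The efficacy and safety analysis will be based on observed values". This says nothing about items within a scale.

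**The concern.** In a sum of recorded scores, a response with no number contributes nothing. On a scale that starts at 0 and where higher is worse, that is the best possible answer. Two subjects who are equally breathless on what they do would get different totals only because one does less. A change in activity between visits would move the total with no change in breathlessness per activity.

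This is more than missing detail. The total is defined, and the definition applied as written gives a figure that does not measure severity of dyspnea alone. The authors specified a rule for the analogous RHS response two items earlier, and the impossible range suggests that the dyspnea paragraph was not checked against the form. At stake are the by-visit dyspnea totals, their trend over Stages 3 and 4, and comparisons across cohorts.

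**Working it through.** **Step 1: reproduce the stated ranges.** For a plain sum, range = (items × lowest code) to (items × highest code). Item counts and codes are from SAP Appendix 1, item 10. Fatigue 8a is taken as 8 items in all, as on the form.

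| Form | Items | Codes | Computed | SAP states |
|---|---|---|---|---|
| Physical Function 20a | 20 | 1–5 | 20–100 | 20–100 |
| Fatigue 8a | 8 | 1–5 | 8–40 | 8–40 |
| Upper Extremity 7a | 7 | 1–5 | 7–35 | 7–35 |
| Dyspnea Severity 10a | 10 | 0–3 | 0–30 | 10–50 |

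Three ranges reproduce; the dyspnea range does not. A range of 10 to 50 would need codes 1 to 5 (10 × 1 to 10 × 5), which neither the SAP nor the form uses for this instrument.

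**Step 2: effect of X under a plain sum.** Assume a subject gives the same score s to every activity done and answers X to m of the ten. The severity values and X counts are assumptions; the documents give no dyspnea data.

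Plain sum = s × (10 − m). Prorated total, in the style of RHS and FSS = (sum of answered items ÷ number answered) × 10, if at least 5 are answered.

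| s | m = 0 | m = 2 | m = 4 | m = 5 | Prorated, each case |
|---|---|---|---|---|---|
| 1 | 10 | 8 | 6 | 5 | 10 |
| 2 | 20 | 16 | 12 | 10 | 20 |
| 3 | 30 | 24 | 18 | 15 | 30 |

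At s = 2, four X responses take 8 points off 20, or 40%. In the other direction, resuming those four activities at unchanged severity raises the total from 12 to 20. With m = 6 only four items are answered, and the prorated total would be missing.

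**Step 3: when the hardest activities are the ones dropped.** Suppose six items score 2 and four score 3: 6 × 2 + 4 × 3 = 24. If the four hard items become X, the plain sum is 6 × 2 = 12. Prorated, it is 12 ÷ 6 × 10 = 20. Proration recovers 8 of the 12 lost points but still sits 4 below 24 (4 ÷ 24 = 17%).

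**Step 4: non-ambulatory subjects.** PROMIS is scheduled for Cohort 2 (protocol Table 11). If the three walking and stair items are X, the highest reachable total is 7 × 3 = 21 out of 30. If they are X at every visit, those items lower the level but produce no trend.

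**The case against.** The strongest reply is that the SAP gives X no value, so counting it as 0 is an inference. A program could set the whole total to missing when any item is X. The 10 to 50 range could also hint at five options coded 1 to 5, and if X took the top code the effect would reverse. It is true that the SAP does not say how X is stored. But where it means a total to be missing it says so, for RHS and FSS, and the same dyspnea bullet states codes 0 to 3. If any X did make the total missing, less active subjects would leave the summary, which is a different selection problem and equally unspecified.

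A reader might also infer that the bias favours treatment. The documents do not support that. Direction depends on whether X responses become more or less common. The study is open-label without a control arm, and the activity-related data shown point to the opposite case: protocol Table 6 gives mean gains in walking distance at Month 18 of 51.7 m (Cohort 1) and 49.0 m (Cohort 3). Subjects who become more active could show a worsening dyspnea total.

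Nor do the documents show that the problem is worst in Cohort 2. Its walking and stair items are likely to be X throughout, which affects level more than change, and SAP Section 6.2.2.4 presents that cohort's efficacy results separately.

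Two further points stand. The items reproduced in Appendix 6 for the other three PROMIS forms carry no X option, so the problem is specific to dyspnea. And the impact is modest: SAP Section 9.1 plans no hypothesis test, and subject listings of each instrument are planned.

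**Conclusion.** The concern holds for the Dyspnea form. Followed as written, the plain sum scores an activity not done like one done without breathlessness, so the total confounds activity with dyspnea in either direction. The 40% difference in Step 2 is an illustration under assumed scores, not an estimate; its size depends on how many items are X and which ones. The conclusion rests on X being skipped in the sum, which is the natural reading of the stated rule but is not explicit. The range error needs no assumption.

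The effect falls on descriptive by-visit totals, trends and cohort displays. Whether it reaches change scores is unclear: SAP Section 9.5 says PROMIS baseline scores will not be available, SAP Section 4.4 still lists change and percent change from baseline, and protocol Section 10.2.9 provides a one-time recall for subjects already on treatment. The point should be corrected, but it does not threaten the study's main conclusions.

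**What to change.** In SAP Appendix 1, item 10, for the Dyspnea form only:

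- State that X is a missing item.
- Apply the 50% response rule already used for RHS and FSS: mean of answered items × 10 if at least 5 of the 10 are answered, otherwise the total is missing.
- Report the number of X responses by visit and cohort. Proration can still understate breathlessness when the hardest activities are the ones skipped (Step 3), and these counts let a reader judge that.
- Correct the range to 0 to 30.

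The cost is a few lines of SAP text and code; the SAP's introduction allows changes until it is finalised before database lock. The downside is that some totals become missing, most often for subjects who do few of the listed activities.
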